6.2 Postoperative Protocol

Pain and Function:

Depression, anxiety, pain at multiple sites, age, and sex have been shown to be associated with pain severity. Demographic information, psychological and medical history, and assessment of pain at multiple sites (using the Widespread Pain Inventory) will be collected or performed at enrollment. Because pain catastrophizing scale (PCS) scores are also associated with pain severity, the PCS will be administered on postoperative day (POD) 2. Furthermore, the following scales will be used to assess pain type and severity at enrollment and at 4 weeks (±3 days), 3 months (±1 week) and 6 months (±4 weeks) postoperatively. If patients initiate rescheduling of the postoperative phone calls, the surveys can be administered outside of the time window. If necessary, patients will be texted with their permission to schedule phone calls or surveys may be emailed to them via REDCap.

- 1. Numerical rating scale (NRS) pain scores (at rest, with movement, worst pain, least pain)
 - 2. The PainDETECT scale a validated measure of neuropathic pain
- 3. The KOOS questionnaire (Symptoms, Pain, Stiffness and Quality of Life subscales) and KOOS Physical Function Shortform a commonly utilized measure of pain and function in patients with knee OA NRS pain scores will also be collected on POD 1 and 2. Attainment of physical therapy goals will be recorded by research assistant on each inpatient day. In the OR, knee flexion and extension measurements will be made via visual assessments with the aid of a goniometer by the surgical team after anesthesia induction. At 6 months following enrollment, patients who developed postoperative joint stiffness and/or persistent chronic postoperative pain will be identified. Postoperative joint stiffness will be defined as ROM≤95 degrees at the 6week (±2 weeks) surgical followup in the postoperative clinic. Persistent postoperative pain will be defined as NRS≥4 with activity in the operated joint at 6 months postoperatively.

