increased preoperative pain severity. Finally, using the novel technology of mass cytometry, a recent study of total hip arthroplasty patients identified a correlation between specific signaling responses in CD14+ monocytes and rates of postoperative recovery of function and resolution of pain (9). Postoperative joint stiffness, which is defined as range of motion (ROM) ≤95 degrees (10), and persistent pain can cause significant morbidity following total knee arthroplasty (TKA). Clinically, risk of postoperative joint stiffness has been associated with factors such as preoperative ROM, younger age, nonwhite race, smoking, high cholesterol, improperly sized components, malalignment, retained osteophytes, and severity of postoperative pain (11,12,13). There is evidence of increased fibroblasts, T cells, mast cells, oxidative stress and activation of the TGFbeta pathway in arthrofibrotic tissue from patients who have undergone total knee arthroplasty (14,15,16). Information is lacking about which inflammatory pathways are active in the perioperative period that may cause persistent postoperative pain and joint stiffness and/or serve as predictors for those patients at highest risk of developing these complications. This study aims to help fill this knowledge gap using targeted tissue analysis as well as unbiased screening methods. By gathering longitudinal clinical data as well as blood, synovial fluid, and tissue samples from OA patients undergoing TKA, we can begin to elucidate risk factors for and inflammatory pathways contributing to persistent pain and/or stiffness compared to those who do not. While it is well known that deregulation of the immune response plays a major role in many autoimmune diseases like RA, the contribution of inflammation to the pathogenesis of OA, disarrayed postarthroplasty healing, and persistent postoperative pain has not been extensively explored. We hypothesize, based on prior studies noted above, that TNFalpha will be elevated in the synovial fluid of patients who develop persistent pain after TKA. In addition, we hypothesize that specific immune signatures predispose patients to develop persistent pain and joint stiffness. Using an unbiased informatics approach to survey complex pathways potentially contributing to adverse outcomes after TKA, we will perform cytokine protein arrays on joint fluid from all patients. In addition, a subset of 30 enrolled patients will be coenrolled as part of a control cohort for the rheumatoid arthritis FLARE study (IRB #13146). Blood and tissue from these patients will be prepared and stored to undergo cellbased analyses (flow cytometry and cytoF), histological examinations (immunohistochemistry), and RNA analysis (nanostring, reverse transcription polymerase chain reaction and RNAseq). Analysis of clinical and biological profiles from OA patients will enable us to better characterize risk factors for and inflammatory pathways contributing to persistent postoperative pain and restricted ROM after TKA. Ultimately, enhanced understanding of such associations has the potential to enable targeting of appropriate preventative interventions to those at highest risk of developing these complications.

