3.0 STUDY HYPOTHESES

1. Elevated levels of TNF-alpha in joint fluid of patients with OA is associated with the risk of development of persistent postoperative pain after TKA.

- 2. Persistent pain (defined as NRS≥4 with activity in the operated joint at 6 months postoperatively) occurs in 10% of patients undergoing TKA for OA.
- 3. Joint stiffness (defined as range of motion [ROM] \leq 95 degrees measured at 6 \pm 2 weeks postoperatively) occurs in 7% of patients undergoing TKA for OA.
- 4. Distinct immune signatures (identified via protein analyses, immunohistochemistry, nanostring, RNA-Seq, fluorescence-activated cell sorting (FACS), and/or mass cytometry [CytoF]) are associated with the risk of developing persistent postoperative pain following TKA in OA patients.
- 5. Distinct immune signatures (identified via protein analyses, immunohistochemistry, nanostring, RNA-seq, FACS, and/or CytoF) are associated with the risk of developing joint stiffness following TKA.
- 6. Demographic profile, comorbidities, psychological factors, pain profiles, pre and postoperative stiffness and inflammatory profiles interact to determine attainment of PT goals and functional outcomes following TKA.

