4.1.2 Secondary Endpoints

- 1. The incidence of postoperative joint stiffness (defined as ROM≤95 degrees) measured at the 6week (±2 weeks) postoperative surgical visit
- 2. Postoperative NRS pain scores measured on POD 1, POD 2, at 4 weeks, 3 months, and 6 months postoperatively
- 3. Postoperative knee ROM measured at 6 weeks (±2 weeks) postoperatively
- 4. Postoperative KOOS and PainDETECT (neuropathic pain assessment) scores measured at 4 weeks, 3 months, and 6 months postoperatively
- 5. Time to attainment of physical therapy goals (Ambulation 40 feet, independent transfer) measured during inpatient stay
- 6. New diagnoses and postoperative medications (recorded during hospital admission, during followup visits, and from postoperative phone followups and chart reviews)

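### Stiffness at 6 weeks is counted without regard to preoperative ROM, so new and pre-existing stiffness are not separated in the frequency or in the marker associations

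*Combined protocol and SAP*

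**What the plan says.** Section 6.2 defines the outcome by a single postoperative reading: "Postoperative joint stiffness will be defined as ROM≤95 degrees at the 6week (±2 weeks) surgical followup in the postoperative clinic". Section 4.1.2 makes it the first secondary endpoint: "The incidence of postoperative joint stiffness (defined as ROM≤95 degrees) measured at the 6week (±2 weeks) postoperative surgical visit". Hypothesis 3 in section 3.0 uses the same cut and timing and expects that stiffness "occurs in 7% of patients undergoing TKA for OA".

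The wording around this endpoint is about onset. Section 6.2 says that at 6 months "patients who developed postoperative joint stiffness and/or persistent chronic postoperative pain will be identified". Hypothesis 5 reads: "Distinct immune signatures (identified via protein analyses, immunohistochemistry, nanostring, RNA-seq, FACS, and/or CytoF) are associated with the risk of developing joint stiffness following TKA". Objectives 1 and 2 in section 2.0 also concern the development of stiffness, and Objective 4 concerns its incidence.

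On the baseline, section 1.0 reports that "risk of postoperative joint stiffness has been associated with factors such as preoperative ROM", the first item in its list of risk factors. Section 6.3 lists knee extension and flexion before, during and after surgery. The eligibility criteria (5.2 and 5.3) require severe radiologic OA and set no ROM limit. Section 7.0 names Firth logistic regression, but it names no covariates and describes no stiffness model. Preoperative stiffness appears as an explanatory factor only in Hypothesis 6, which concerns physical therapy goals and functional outcomes.

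**The concern.** An absolute cut at 6 weeks describes who is stiff after surgery. It does not show who became stiff. A knee with an 85-degree arc before surgery and 92 degrees at 6 weeks has improved, yet it enters the case group on the same footing as a knee that fell from 120 to 92.

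This matters most for the marker analyses. Section 6.1 has joint fluid aspirated before arthrotomy and baseline blood drawn before incision, when any existing restriction is present. A marker that tracks restriction in the arthritic knee can then show an association with 6-week stiffness even if it has nothing to do with stiffness arising after the operation. The stated aim is to find pathways that contribute to these complications, so the two explanations lead to different conclusions. With few stiffness cases expected, a handful of carried-over knees would change the case group noticeably.

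**Working it through.** **1. The plan's own figure.** The only calculation in section 7.0 is for pain: N = (z₀.₉₇₅ + z₀.₈)² / [p(1−p)(ln OR)²] / (1−R²). With p = 0.10, OR = 2.49 and R² = 0.3, this is 7.849 / (0.09 × 0.8323) / 0.7 = 149.7, so the stated 150 reproduces with two-sided alpha. There is no corresponding calculation for stiffness, and nothing below alters this one.

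**2. Expected stiffness cases.** At 7%: 0.07 × 150 = 10.5; 0.07 × 161 = 11.3 (161 being 179 less 10% exclusions); 0.07 × 179 = 12.5.

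**3. Share of cases that are pre-existing.** The documents give no distribution of preoperative ROM. Assume that preoperative and 6-week ROM are bivariate normal, with preoperative mean m = 110-120, SD 15 and correlation ρ = 0.3-0.5, calibrated to 7% at or below 95 degrees at 6 weeks. Then:
- share stiff before surgery: q = Φ((95 − m)/15)
- stiff at both times: J = Φ₂((95 − m)/15, Φ⁻¹(0.07); ρ)
- pre-existing share of cases: J / 0.07
- new-onset risk among knees above 95 degrees before surgery: (0.07 − J) / (1 − q)

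| m | ρ | q | J | pre-existing share | new-onset risk |
|---|---|---|---|---|---|
| 120 | 0.3 | 4.8% | 0.90% | 13% | 6.4% |
| 120 | 0.5 | 4.8% | 1.49% | 21% | 5.8% |
| 110 | 0.3 | 15.9% | 2.30% | 33% | 5.6% |
| 110 | 0.5 | 15.9% | 3.36% | 48% | 4.3% |

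In 179 patients this is 179 × J = 1.6 to 6.0 of the 12.5 expected cases.

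**4. Sensitivity to the form of the assumption.** Instead, set q directly, and let s be the chance that a knee stiff before surgery is still at or below 95 degrees at 6 weeks. With q = 2% and s = 20%, the share is 0.004 / 0.07 = 6% and new-onset risk is (0.07 − 0.004) / 0.98 = 6.7%. With q = 10% and s = 50%, the share is 0.05 / 0.07 = 71% and new-onset risk is (0.07 − 0.05) / 0.90 = 2.2%. The range is wide because the inputs are unknown.

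**5. Effect on a marker analysis.** Under the model in step 3, take a marker correlated with preoperative restriction but with no effect of its own on 6-week ROM. Simulated Firth penalised likelihood-ratio tests (n = 161, 800 replicates per setting) reject in 7-11% of trials when that correlation is 0.2, and in 11-27% when it is 0.4. With preoperative ROM in the model they reject in 4.5-5.6%.

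**6. Which mechanism dominates.** Restrict the same model to knees above 95 degrees before surgery. Between 57% and 78% of the marker difference between stiff and non-stiff knees remains. Removing already-stiff knees therefore deals with the smaller part; most of the distortion is confounding by ROM on its continuous scale.

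**The case against.** The strongest reply is that an absolute cut is a legitimate definition. Section 1.0 takes it from a cited source, it is applied consistently, and postoperative stiffness can simply mean being stiff once the joint has been replaced. That stands, and the endpoint should be kept.

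Three further points stand:
- A reader might infer that the 7% in Hypothesis 3 is inflated. It is not: the expected and observed rates use the same definition. The lower figures in step 3 answer a different question.
- A reader might infer that the protocol ignores preoperative stiffness altogether. Hypothesis 6 does use it, though only for physical therapy goals and function, so it does not reach the stiffness endpoint or Hypothesis 5.
- The rejection rates in step 5 are false positives only for an effect independent of preoperative ROM. Hypothesis 5 says that signatures "are associated with the risk of developing joint stiffness following TKA", and a marker that works through preoperative ROM is truly associated and may be useful for prediction. If inflammation itself causes preoperative restriction, ROM is a mediator, and adjustment removes part of the pathway under study.

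What does not stand is that the unnamed model covariates in section 7.0 might already include ROM. They appear only in the sample size statement for TNF-alpha and pain.

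**Conclusion.** The concern holds in a limited form. The definition does not separate new from pre-existing stiffness, and no stiffness endpoint or stiffness analysis uses a baseline that the protocol both names as a risk factor and records. The 7% is therefore not a new-onset rate, and a marker association with stiffness cannot, as planned, be read as an association with developing it.

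The size and direction of any distortion cannot be determined from the documents. The figures of 13-48% pre-existing cases and 4.3-6.4% new-onset risk depend entirely on the assumed mean, SD, correlation and normality, and the second set of assumptions gives 6-71%. It would go too far to conclude that marker findings will be spurious, or that miscounted knees are the main problem. In the model used here, the missing adjustment for continuous ROM matters more.

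The endpoint is secondary. The primary pain endpoint and its sample size are not affected.

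**What to change.** In sections 4.1.2 and 6.2, keep ROM at or below 95 degrees at 6±2 weeks as the endpoint, and report its frequency overall and separately for knees at or below and above 95 degrees before surgery.

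In section 7.0, for Objectives 1 and 2 and Hypothesis 5, report each stiffness-marker model twice: unadjusted, and with preoperative ROM as one continuous covariate. Claim an association with developing new stiffness only from the adjusted result. The unadjusted result may be described as an association with being stiff at 6 weeks.

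Use the preoperative/baseline flexion and extension listed in section 6.3, and state how they were taken. The only method described is for the operating room, where "knee flexion and extension measurements will be made via visual assessments with the aid of a goniometer by the surgical team after anesthesia induction"; a reading after induction may not be comparable with the clinic reading. A reader might assume that the baseline reading is taken awake, but the documents do not say so.

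No new visit or measurement is needed, since the fields are already on the data collection list; the method of the baseline reading has to be confirmed. The statistical cost is one degree of freedom with about 11-13 events. If preoperative restriction is itself a result of inflammation, the adjusted estimate removes that pathway, which is why both models should be shown.

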1.0 INTRODUCTION

The primary condition being studied is persistent pain following total knee arthroplasty (TKA) performed for knee osteoarthritis (OA). Published literature suggests that persistent postarthroplasty pain occurs in 1040% and joint stiffness requiring intervention occurs in 1040% of such patients and can adversely impact function and quality of life. This study is designed to test whether there is an association between joint fluid TNFalpha levels and development of persistent postoperative pain. The secondary condition being studied is joint stiffness following TKA performed for OA. Persistent pain can interfere with participation in physical therapy and may predispose patients to joint stiffness. Reciprocally, inflammation contributing to joint fibrosis and stiffness may also cause persistent postoperative pain. This study has the potential to shed light on the interaction between clinical, demographic and biological factors contributing to persistent postarthroplasty pain and joint stiffness in patients with knee OA.

Approximately 4 million Americans have undergone total knee arthroplasty (Weinstein AM et al., Estimating the burden of total knee replacement in the United States. J Bone Joint Surg Am 2013;95:38592), and persistent postoperative pain and joint stiffness may cause significant morbidity in up to 40% of these patients. This project aims to identify inflammatory pathways that contribute to and predict development of these complications. Identification of such pathways may allow us to target preventative measures to the patients at highest risk of persistent postoperative pain and joint stiffness.

[figure not shown]

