- Worst NRS pain score in operative knee in past 24 hours
- Least NRS pain score in operative knee in past 24 hours
- PCS questionnaire
- PainDETECT questionnaire
- KOOS Knee survey
- Pain Questionnaire

- Quality of Life Questionnaire
- KOOS Physical Function Shortform
- Blood draw completed? (Y/N; Why)
- Blood draw arterial or venous?
- Blood drawn from side with IV? (Y/N; Why)
- Plasma aliquoted and stored? (Y/N)
- Blood hemolyzed (red plasma)? (Y/N)
- Was IV TXA administered either intraoperatively or postoperatively?
 (Y/N; dose)
 - Changes from default TKA postop protocol? (Y/N)
- Was there escalation from the postoperative pain protocol at any point during the inpatient stay? (Protocol: PCEA with standard settings, oxycodone or hydrocodone 510 mg q4h prn, PO or IV acetaminophen standing dose or prn, meloxicam. E.g., needing higher doses, needing extra days of PCEA, addition of a new class of medication such as gabapentinoids, etc.) (Y/N)
 - Epidural PCA Placement Time
 - Epidural PCA Removal Time
 - Time Epidural PCA Was in Place
 - Did the patient require IV PCA? (Y/N)
 - Time to ambulation of 40 feet (with or without assistance)
 - Time to independent transfer (sitstand)
 - Postoperative joint stiffness? (Y/N)
 - Was manipulation performed for joint stiffness?
 - Postoperative persistent pain? (Y/N)

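### The stiffness endpoint is a single range-of-motion reading at 6 weeks, so a knee already manipulated for stiffness that then measures above 95 degrees counts as not stiff

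*Combined protocol and SAP*

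**What the plan says.** Three places in the combined protocol and SAP set the same rule. Section 4.1.2 lists as the first secondary endpoint "The incidence of postoperative joint stiffness (defined as ROM≤95 degrees) measured at the 6week (±2 weeks) postoperative surgical visit". Section 6.2 repeats it: "Postoperative joint stiffness will be defined as ROM≤95 degrees at the 6week (±2 weeks) surgical followup in the postoperative clinic". Hypothesis 3 in section 3.0 attaches an expected rate to that rule, saying that stiffness so defined "occurs in 7% of patients undergoing TKA for OA". The background in section 1.0 uses the same 95-degree cut-off.

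Section 6.3 and the synopsis collect a separate post-operative item, "Was manipulation performed for joint stiffness". No date is listed with it, and no section links it to the endpoint. The plan does not say whether a manipulated knee counts as stiff, whether its pre-manipulation ROM is used, or whether a sensitivity analysis is done. Section 7.0 mentions neither stiffness nor manipulation.

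Section 6.2 also says what the classification is for: "At 6 months following enrollment, patients who developed postoperative joint stiffness and/or persistent chronic postoperative pain will be identified".

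**The concern.** The stated aim is to find patients who developed stiffness. The stated rule looks once, between weeks 4 and 8, and takes the reading as it stands. If a knee has already been manipulated for stiffness, that reading is a post-treatment value. A good response to treatment then turns a patient treated for stiffness into a non-stiff one.

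Two analyses are exposed. The incidence under hypothesis 3 leaves such a patient out of the numerator. The marker comparison under hypothesis 5 places the patient among the controls. Few events are expected, so a handful of such knees would be a visible share of the cases. If the manipulation date is not captured, an analyst cannot later tell which ROM readings were taken after treatment.

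**Working it through.** **Inputs from the documents.** ROM-defined stiffness rate 7% (section 3.0). From section 7.0: pain rate 10%, odds ratio 2.49 per SD, R² 0.3, alpha 0.05, power 0.8, allowance for exclusions 10%, 179 enrolled.

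**1. The plan's own sample size.** For logistic regression on one continuous covariate,

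n = (z₀.₉₇₅ + z₀.₈)² / [p(1−p)(ln OR)²] / (1−R²) = (1.960 + 0.842)² / [0.10 × 0.90 × 0.912²] / 0.7 = 104.8 / 0.7 = 149.7, so 150.

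The stated 150 reproduces with a two-sided test. It was set for persistent pain, so the stiffness rule does not touch it.

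**2. Weight of one knee.** With the 10% allowance taken off, 179 × 0.9 = 161.

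| Patients | Events at 7% | One knee as share of events | One knee in incidence |
|---|---|---|---|
| 161 | 11.3 | 1/11.3 = 8.9% | 1/161 = 0.62 points |
| 179 | 12.5 | 1/12.5 = 8.0% | 1/179 = 0.56 points |

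**3. If further knees are manipulated early.** The 7% belongs to the ROM rule, so early-manipulated knees that measure above 95 degrees come on top of it. How many there are is an assumption. The last column is the odds ratio detectable with 80% power, exp{2.80 / √[N p(1−p)(1−R²)]}, with N = 179 and the plan's R² of 0.3. It shows only what the event count is worth.

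| Extra knees (assumed) | Composite rate | Events of 179 | Share missed by ROM alone | Detectable OR |
|---|---|---|---|---|
| 0% | 7% | 12.5 | 0% | 2.67 |
| 1% | 8% | 14.3 | 1/8 = 12.5% | 2.52 |
| 2% | 9% | 16.1 | 2/9 = 22% | 2.40 |
| 3% | 10% | 17.9 | 3/10 = 30% | 2.30 |

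**4. Effect on a marker association under the ROM rule.** These are Firth logistic simulations with 161 patients, one standardised marker, no covariates and 1,200 replicates. The odds ratio of 2.49 is borrowed from the pain endpoint, because the plan gives none for stiffness.

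- *7% is the ROM-only rate; 1% to 3% more are manipulated early, at random with respect to the marker.* Power was about 77%, against 79% at 7% with no misclassification. The median odds ratio was 2.35 to 2.38, against 2.42. A repeat run gave 74% to 78% power, the lowest value at 3%.
- *7% is instead the total, with 20% or 40% of stiff knees lost at random.* Power falls from 78% to 66% or 57%, but the odds ratio only from 2.45 to 2.38 in both cases. The loss comes mainly from fewer events. At 40%, 0.4 × 11.3 = 4.5 knees join 161 × 0.93 = 149.7 controls, so they are 4.5/154.2 = 2.9% of the control group.
- *As above, but the lost knees are exactly those with the highest marker values.* The odds ratio falls to 1.68 or 1.25 and power to 29% or 6%. This is an extreme bound.

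**The case against.** The strongest reply is that the mechanism is not shown to occur. It needs a manipulation before the visit and then a reading above 95 degrees. The 6-week surgical follow-up is the earliest postoperative clinic visit that the documents name, and the 4-week contact is a survey. That stands as to size: the count could be zero. It does not settle the rule, because the window runs to week 8 and earlier manipulation is not excluded.

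A second reply is that a fixed-time ROM endpoint is objective and matches the background. Section 1.0 does define stiffness as ROM of 95 degrees or less. A reader might infer from "joint stiffness requiring intervention occurs in 1040% of such patients" that the plan defines stiffness by treatment, but that sentence reports a literature rate (its range has lost a dash). Nor do the documents give a ROM threshold for manipulation, so a manipulated knee need not have met the cut-off beforehand. These points justify keeping the ROM endpoint. They do not justify using a knee treated for stiffness only as a non-stiff control.

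A third reply is that the manipulation item and the medical record allow later reclassification. They do, which makes the fix cheap. Without a rule set in advance, however, the choice would be made after the fact on about a dozen events.

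**Conclusion.** The point holds as a defect in how a secondary endpoint is classified. The wording places a knee successfully manipulated for stiffness by the visit in the non-stiff group, against the stated aim of identifying patients who developed stiffness. Each such knee equals about 8% to 9% of the expected events and about 0.6 points of incidence. That rests on the plan's 7% and on 161 to 179 evaluable patients. How many knees are affected cannot be learned from the documents.

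Two stronger readings are not supported. A reader might infer that the observed incidence would drop well below 7%, for example to 5.6% or 4.2% if 20% or 40% of stiff knees were lost. That treats 7% as the rate of all stiffness, whereas section 3.0 gives it for the ROM rule itself. A reader might also infer that marker associations would be pulled strongly toward the null. Random loss barely moves the odds ratio. The marked attenuation arises only if early manipulation is related to marker level, and nothing in the text suggests that the highest-marker knees are the ones treated early. Lost events and some lost power are the harm to expect.

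The primary endpoint and its sample size are unaffected.

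**What to change.** Before the marker analysis, abstract the date of any manipulation for stiffness from the medical record, which the synopsis already names as a data source. State in sections 3.0, 4.1.2 and 6.2 that stiffness will be reported in two ways, side by side, for both the incidence and the marker associations:

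1. ROM of 95 degrees or less at the 6-week (±2 weeks) visit, as now.
2. ROM of 95 degrees or less at that visit, or manipulation for stiffness on or before it.

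Also report how many knees the two classifications place differently. If none do, the question is closed.

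The cost is one chart date per manipulated knee, a short addition to the text and one extra analysis. Because the text already records 179 patients enrolled, the addition should be dated and documented as made before marker results are compared with outcome. The drawback is that the second classification includes a surgeon's decision to manipulate, which may vary between the participating surgeons; the ROM-only result alongside shows how much that matters. This concerns endpoint classification only and takes no position on when manipulation should be done.
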